7.0 STUDY MEDICATION

7.1 Investigational Drug Supply

Bausch Health will provide study drug to the sites. The drug provided will be specifically labeled as clinical trial materials for this study, utilizing a label on both the primary foil pouch and the carton. The carton will be closed and secured with tamper evident tape.

Pegaptanib sodium drug substance is a pegylated (40 kDa branched PEG molecule consisting of two 20 kDa PEG arms) anti-VEGF aptamer. It is formulated in phosphate

buffered saline at pH 6-7. Sodium hydroxide or hydrochloric acid may be added for pH adjustment.

The drug product is supplied in a sterile foil pouch as a single-use glass pre-filled syringe. After proper preparation, the syringe will contain 0.3mg of Macugen[®] in a nominal 90µL deliverable volume pack. A sterile packaged BD[®] single use 30G X ½” Precision Glide[®] Luer Lok[®] needle is supplied in a separate pouch. The foil pouch and needle are packaged together in a carton. For a full description of the drug product, please review the package insert located in [Appendix 1](#).

Active Ingredient:	Pegaptanib Sodium Injection formulated as: 3.47mg/mL solution to deliver a dose of 0.3mg pegaptanib sodium injection
Excipients:	Sodium Chloride, USP Sodium Phosphate Monobasic, Monohydrate, USP Sodium Phosphate Dibasic, Heptahydrate, USP Sodium Hydroxide, USP (as needed) Hydrochloric acid, USP (as needed) Water for injection, USP

7.2 Dose and Administration

7.2.1 Preparation

The drug product, pegaptanib sodium, is a ready-to-use sterile solution provided in a single-use glass syringe. Ensure that the drug to be administered is labeled specifically for this study. Preparation of the syringe for drug administration includes the following steps (see [Appendix 1](#) for more details):

1. Remove the syringe from the plastic clip.
2. Twist off cap.
3. Attach the sterile administration needle (included) to the syringe by screwing it into the syringe tip. Another sterile administration needle may be used in lieu of the one included. Remove the plastic needle shield from the needle.
4. Holding the syringe with the needle pointing up, check the syringe for bubbles. If there are bubbles, gently tap the syringe with your finger until the bubbles rise to the top of the syringe. SLOWLY depress the plunger rod to eliminate all the bubbles and to expel the excess drug so that the top edge of the 3rd rib on the plunger aligns with the pre-printed black dosing line.
5. Inject the entire contents of the syringe.

7.2.2 Treatment Regimen and Duration

Pegaptanib sodium will be administered as 90µl (nominal delivered volume) intravitreal injections every 6 weeks from Day 0 to Week 48 as described in Section 3, Study Flow Chart.

7.2.3 Administration of Study Drug and Controls

The method for intravitreal administration of pegaptanib sodium is described in [Appendix 1](#).

7.2.4 Stability of Final Solution

The drug product should be used without further dilution. Expiration dating will be based on available stability information and will not exceed what is approved for the commercial product.

7.2.5 Storage of Drug product

The Investigator, or an approved representative (e.g. pharmacist), will be using the drug supplied by Valeant Pharmaceuticals NA. The Investigator or representative will be asked to document treatments given to each patient during each visit. The drug will be stored in a secured area, under recommended storage conditions and in accordance with applicable regulatory requirements. The pegaptanib sodium is to be stored under standard refrigeration conditions (2-8°C; 36-46°F) and not frozen.

7.3 Previous or Concomitant Medications and Restrictions

Any treatment with any investigational agent for any condition in the past 30 days is not permitted. Additional therapy during the study, with a therapy of the Investigator's choosing (except Macugen[®]), may be employed at the Investigator's discretion for circumstances judged to be clinical deterioration, *such as but not restricted to*: ≥ 2 line vision loss; retinal thickness at center point ≥ 300 μm ; an increase in retinal thickness of 100 μm from baseline visit. Additional treatment of a non-VEGF agent may be given on any day the Investigator prefers. It is recommended that additional treatment with another VEGF agent should be given at least 3-weeks after a Macugen[®] (pegaptanib sodium injection) injection unless the Investigator does not feel this is in the best interest of the subject.

8.0 STUDY CONDUCT

8.1 Study Evaluations

Written informed consent must be obtained before any of the Baseline procedures listed below are performed. An explanation of the study and discussion of the possible risks and discomforts will be given by the Investigator. Only those subjects who fulfill all eligibility criteria will be entered into the study.

The following assessments will be performed at Baseline and during the treatment and follow-up periods. All visits for injections must occur within +/- 14 days of the schedule.

8.1.1 Baseline Visit

The following Baseline evaluations, as outlined in the Study Flow Chart (see Section 3), will be performed within 7 days prior to receiving Macugen[®] (Pegaptanib Sodium injection). Baseline assessments can be broken into 2 days if necessary. If all screening is completed during the baseline visit, DAY 0 assessments may be done on the same day.

Valeant Pharmaceuticals

- Informed consent
- Medical history
- Ophthalmologic/AMD history
- Urine pregnancy test within 7 days of first injection (if applicable)
- Concomitant Medication Assessment and Serious Adverse Events

8.1.2 Day 0

The following assessments will be performed at the Day 0 Visit.

- Macugen[®] (Pegaptanib Sodium injection) administration
- Corneal Specular Microscopy (Both eyes). Send results to CIARC
- Concomitant Medication Assessment and Adverse Events

8.1.3 Week 6, Week 12, Week 18, Week 30, Week 36, Week 42, Week 48

The following assessments will be performed at the Visit:

- Macugen[®] (Pegaptanib Sodium injection) administration
- Concomitant Medication Assessment and Adverse Events

8.1.4 Week 24

The following assessments will be performed at the Visit:

- Macugen[®] (Pegaptanib Sodium injection) administration
- Corneal Specular Microscopy (Both eyes). Send results to CIARC
- Concomitant Medication Assessment and Adverse Events

8.1.5 Week 54

The following assessments will be performed at the Visit:

- Corneal Specular Microscopy (Both Eyes). Send results to CIARC
- Concomitant Medication Assessment and Adverse Events

8.1.6 Early Termination Visit

Due to the critical nature of the corneal specular microscopy data set, any patient who discontinues from the study early outside of a scheduled clinic visit, the study doctor will need to notify the Sponsor for further instruction. The Sponsor should also be notified if a patient is not expected to complete the study.

8.2 Protocol Compliance and Violations

The protocol must be read thoroughly and the instructions should be followed exactly. Either the Sponsor or the Investigator without agreement by both parties will not implement modifications to the study protocol. However, the Investigator may implement a deviation from, or a change of, the protocol to eliminate an immediate hazard(s) to the study subjects without prior IRB/Sponsor approval/favorable opinion. As soon as

possible, the implemented deviation or change, the reasons for it and, if appropriate, the proposed protocol amendment should be submitted to the IRB/Sponsor. Significant protocol deviations or violations may require that the subject be withdrawn from the study. The Investigator is responsible for notifying the IRB of all protocol deviations or violations.

8.3 Subject Discontinuation

Subjects have the right to withdraw from the study at any time for any reason. The Investigator (after consultation with the Sponsor) or Sponsor also have the right to withdraw subjects from the study in the event of concurrent illness, adverse events, treatment-failure after a prescribed procedure, protocol violations, cure, administrative or other reasons. Every reasonable attempt should be made to encourage the subject to return at Week 54 for evaluation.

Final study assessments as outlined in the Study Flow Chart, Section 3, should be performed on all subjects who withdraw. Subjects who withdraw due to an adverse event should be followed until resolution of the adverse event, or an adequate explanation for the event is obtained.

Subjects who withdraw for any reason should have assessments performed according to the Early Withdrawal schedule.

8.4 Study Discontinuation

The reason for a subject discontinuing from the study will be recorded in the case report form. A discontinuation occurs when an enrolled subject ceases participation in the study, regardless of the circumstances, prior to completion of the protocol. The Investigator must determine the primary reason for discontinuation. A discontinuation must be reported immediately to the Sponsor or his/her designated representative if it is due to a serious adverse event (SAE) (see Section 11). The final evaluation required by the protocol will be performed at the time of study discontinuation. The Investigator will record the reason for study discontinuation, provide or arrange for appropriate follow-up (if required) for such subjects, and document the course of the subject's condition.

Premature termination of this clinical study may occur because of a regulatory authority decision, change in opinion of the IRB/EC, product or procedure safety problems, or at the discretion of the Sponsor.

9.0 OUTCOME MEASURES

9.1 Safety Measurements and Endpoints

9.1.1 Corneal Specular Microscopy

A post marketing study commitment was made to the FDA stating that the sponsor would, "provide clinical information from a 1-year (minimum) clinical study to support that there are no adverse effects on the corneal endothelium following the intravitreal administration of Macugen[®]." Corneal specular microscopy data will be collected on an enrollment of approximately 125 subjects in order to fulfill the commitment made to the FDA. Assessments of specular microscopy of the corneal endothelium will be completed and compared individually for central cell density and cell characteristics changes (polymegathism and polymorphism) occurring from baseline. All 10 targeted clinical sites will perform Corneal Specular Microscopy assessments on approximately 125 enrolled subjects. Both contact and non-contact microscopes are permitted, but consistency throughout the entire study is required

(same method must be used for each subject at any given site). Corneal Specular Microscopy examinations must be performed at Baseline and at Weeks 24 and 54 or early withdrawal.

The study sites will perform the corneal specular microscopy assessment in accordance with the protocol and the Corneal Specular Microscopy Instruction Manual. At baseline, Week 24, Week 54 or early withdrawal, the site will send all the data to CIARC within 3 days of collection. At the completion of the study, CIARC will perform a final analysis of the corneal specular microscopy data. CIARC will calibrate and certify study site Specular Microscopes. For complete procedures for specular microscopy of the corneal endothelium, please refer to the Corneal Specular Microscopy Instruction Manual.

9.2 Efficacy Measurement and Endpoints

This is a safety study and no primary efficacy endpoint is defined. The effect on the corneal endothelium will be assessed by specular microscopy: Mean cell density loss from baseline over time and frequency distribution.

10.0 STATISTICAL METHODS

10.1 Determination of Sample Size

In order to fulfill a commitment to FDA, at least 100 subjects will need to complete the study. To achieve this number of completed subjects, approximately 125 subjects will be enrolled to account for possible early withdrawals.

10.2 Methods of Analysis

The objective of this study will be to assess the effect of intravitreal injections of Macugen[®] (pegaptanib sodium injection) administered every 6 weeks for 48 weeks on the corneal endothelium. The primary analysis will be carried out when all subjects have reached their Week 54 assessment.

10.2.1 General Statistical Methods

Categorical data will be summarized using frequency tables, presenting the patient counts and the percentage of patients falling into the category. McNemar's chi-square may be used to assess within-subject change in a bivariate response variable.

Confidence intervals will be constructed using traditional large-sample methodology.

The SAS system will be used to perform all analyses.

A final data analysis plan will be developed prior to locking the CRF database at the conclusion of the study. The statistical plan will include mock-ups of all tables, listings, and figures to be included in a summary report, as well as documentation of all data derivations and statistical methods utilized, including any deviations from those described here.

All statistical analyses will be performed by a statistical office independent of the study Sponsor.

10.2.2 Safety Data Analysis

The safety analysis will be conducted on all subjects who had at least one administration of the study drug. Adverse events will be summarized using MedDRA

terms. The incidence and severity of adverse events will be listed and grouped by body system.

Summary statistics will be given on the number of subjects for whom the study medication had to be reduced or permanently stopped.

Safety endpoints are:

- All adverse events reported, whether deemed related to treatment or not
- All serious adverse events (SAE) reported, whether deemed related to treatment or not

11.0 DRUG SAFETY

11.1 Definition of Adverse Event

An adverse event (AE) is defined as any untoward medical occurrence in a subject administered a pharmaceutical product and which does not necessarily have to have a causal relationship with the treatment. Therefore, any unfavorable, unintended and emergent medical sign (including an abnormal laboratory finding), symptom, or disease temporally associated with the use of study medication must be reported whether or not considered related. Furthermore, in addition to events not present prior to exposure, any event already present that worsens in intensity or frequency following exposure to study medication must also be reported. All AEs, whether or not they are considered related to the product or device are to be recorded in the subject's medical record and the CRF.

The definitions and terminology to be used during the study are those that reflect the International Conference on Harmonization (ICH E6 (R2)) of Technical Requirements for Registration of Pharmaceuticals for Human Use Guidelines for Good Clinical Practice (GCP).

Each subject eye treated must be examined for the presence/absence of adverse events at all visits, whether scheduled or not. If an adverse event occurs, the first concern will be the safety and welfare of the subject; treatment should be provided as appropriate for the event. Depending on the severity and attribution of the event to the investigational device, FDA regulations and GCPs determine how incidences of safety events are to be recorded and/or reported during the study.

11.1.1 Relationship of Adverse Events

The assessment of the relationship of an AE to the administration of study procedure is a clinical decision based on all available information at the time of the completion of the CRF. In this study, adverse events will be assessed for their relationship to the study drug.

The relationship to study treatment (administrative procedure or (drug)) will be assessed using the following definitions.

Related = There is at least a reasonable possibility that the AE/SAE is related to the study drug. Reasonable possibility means that there is evidence to suggest a causal relationship between the drug and the AE.

Not Related = There is little or no reasonable possibility that the AE/SAE is related to the study drug. This assessment implies that the AE/SAE has little or no temporal relationship to the study drug and/or a more likely or certain alternative etiology exists.

Events may be attributed to either the administrative procedure of the protocol or the drug (and not both), or to neither.

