4.3.1.2 Macugen for Treatment of Diabetic Macular Edema (DME)

EOP1002 was an open label study of intravitreal injections of 3 mg pegaptanib sodium/eye every 6 weeks for up to 36 weeks in ten (10) patients with diabetic macular edema (DME). No dose limiting toxicities were reported and there were no premature withdrawals from the EOP1002 study due to treatment-related AEs. A total of 69 AEs were reported, 29 of which were considered treatment related. Treatment-related AEs were mostly (28/29 reports) due to the injection procedure. There were 5 SAEs experienced by two subjects, with one subject dying 26 days after the last injection of study treatment due to multisystem organ failure and pneumonia. None of the SAEs was considered treatment-related.

A phase 2 dose-ranging study, EOP1005 was conducted to evaluate safety and efficacy of Macugen[®] (pegaptanib sodium injection) in the treatment of diabetic macular edema (DME) [11]. This was a randomized, double-masked, multicenter, dose-ranging, controlled trial. Intravitreal pegaptanib sodium (0.3 mg, 1 mg, 3 mg) or sham injections were given at study entry, week 6, and week 12 with additional injections and/or focal photocoagulation as needed for another 18 weeks. Final assessments were conducted at week 36. A total of 172 subjects were enrolled. Median VA was better at week 36 with pegaptanib sodium 0.3 mg (20/50), as compared with sham (20/63) ($P = 0.04$). A larger proportion of those receiving 0.3 mg gained VAs of ≥ 10 letters (approximately 2 lines) (34% vs. 10%, $P = 0.003$) and ≥ 15 letters (18% vs. 7%, $P = 0.12$). The results of this exploratory Phase 2 study did not identify any safety concerns for the treatment of patients with DME. Pegaptanib sodium was generally well tolerated. The safety profile in this study appears similar to that established in the

age-related macular degeneration (AMD) indication, with additional findings consistent with what would be anticipated in a diabetic population.

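### Section 11.1.1 calls for procedure-relatedness but defines relatedness for the drug only and bars joint attribution, so causality can be coded inconsistently across sites

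*Combined protocol and SAP*

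**What the plan says.** Section 11.1.1 sets the scope of the causality assessment several times, and the statements differ.

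- It opens by describing the assessment as one of relationship to the administration of the study procedure.
- It then narrows this to the drug: "In this study, adverse events will be assessed for their relationship to the study drug."
- It widens it again: "The relationship to study treatment (administrative procedure or (drug)) will be assessed using the following definitions."
- The definitions that follow are worded for the drug alone: "Related = There is at least a reasonable possibility that the AE/SAE is related to the study drug". Not Related covers an event with "little or no temporal relationship to the study drug and/or a more likely or certain alternative etiology exists".
- It ends with the single-choice rule: "Events may be attributed to either the administrative procedure of the protocol or the drug (and not both), or to neither."

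Elsewhere, section 10.2 restates the objective, which is to "assess the effect of intravitreal injections of Macugen" on the corneal endothelium. Section 10.2.2 makes the safety endpoints independent of causality. The first is "All adverse events reported, whether deemed related to treatment or not", and the second says the same for serious events. Section 11.1 requires every AE to be recorded whatever its attribution. It also says, in wording written for an investigational device, that severity and attribution bear on how safety events are recorded or reported.

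**The concern.** The question put to this study is about the injections, so drug and procedure together. The regulatory commitment quoted in section 9.1.1 likewise concerns effects after intravitreal administration. A drug-only definition of Related does not match that question.

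The overlap between the two causes is real in the protocol's own background. Section 4.3.1.1 lists corneal edema and anterior chamber inflammation among the study-eye events seen in at least 10% of treated subjects in the pivotal trials. It also says that investigators ascribed most ocular events to the procedure. For EOP1002, section 4.3.1.2 reports: "Treatment-related AEs were mostly (28/29 reports) due to the injection procedure." An investigator here will often face an event that could come from the needle, the preparation, the drug or a combination. With a single arm, no comparison group can separate them later.

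Two things are at stake. Ten sites may code the same kind of event differently. And an event that meets the stated threshold for a drug relationship may still be denied that attribution because the procedure was chosen.

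**Working it through.** The plan states no figure on this point, so the check is mainly a reading of the text. Two small calculations show the possible size.

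**Step 1. Apply the definitions and the closing sentence to the same events.**

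| Investigator's view of the event | Definitions read literally (drug only) | Closing sentence |
|---|---|---|
| Drug only | Related | Drug |
| Procedure only | Not Related, if the procedure counts as an alternative etiology | Procedure |
| Reasonable possibility of both | Related, since the drug threshold is met | Drug or procedure, not both |
| Neither | Not Related | Neither |

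The two readings agree on the first and last rows and can disagree on the middle two. Nothing in section 11.1.1 says which prevails. No definition exists for the procedure column that the closing sentence creates.

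**Step 2. Effect of barring joint attribution.** Let d events be drug only, p procedure only, and m have a reasonable possibility of both. With two independent items, the drug count would be d + m and the procedure count p + m. Under the closing sentence, suppose k of the m mixed events go to the drug, with k between 0 and m.

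- Recorded drug count: d + k, short by m − k.
- Recorded procedure count: p + (m − k), short by k.
- Either cause: (d + k) + (p + m − k) = d + p + m, unchanged.

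The drug count therefore falls by anything from 0 to m. The documents give neither m nor k. The either-cause total is preserved, but only if sites follow the closing sentence.

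**Step 3. Extreme illustration from EOP1002 (section 4.3.1.2).** Inputs: 69 AEs, 29 treatment-related, 28 of those due to the procedure.

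- Share of AEs treatment-related: 29/69 = 42.0%.
- Procedural share of those: 28/29 = 96.6%.
- Coded by the closing sentence: 28 procedure, 1 drug (assuming that the remaining event is a drug attribution), and 69 − 29 = 40 neither. Either cause stays at 29/69 = 42.0%.
- Coded by the literal drug-only definition: 1/69 = 1.4% Related if none of the 28 also had a possible drug cause, rising to 29/69 = 42.0% if all did.

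The range of 1 to 29 shows how far the result depends on the sentence followed and on an unstated overlap. It does not predict this study. EOP1002 had ten DME patients at 3 mg, against 0.3 mg here, and the protocol does not say that any of the 29 events was corneal.

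**Step 4. Which planned results use the code.** The AE and SAE endpoints in section 10.2.2 count events regardless of relationship. The corneal endpoint in sections 9.1.1 and 9.2 is cell density by specular microscopy, which has no causality field. Section 10.2.2 names no related-event table. Section 10.2.1 leaves derivations and table mock-ups to a later data analysis plan.

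**The case against.** The strongest reply is that the closing sentence itself names the procedure as an attribution distinct from neither. The opening sentence and the lead-in to the definitions also provide for it. On that reading an injection-caused event is coded to the procedure and nothing is lost. This stands against a stronger claim that a reader might infer: that injection-caused corneal events are, as a rule, recorded as Not Related. The documents do not support that. It is one literal reading of the definitions, and the CRF fields are not shown.

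A reader might also infer that the drug-related count is systematically biased downward. That is not supported either. Joint attribution is barred, but no text says which cause prevails, and the low threshold for Related could pull a mixed event towards the drug. The count can fall; the documents do not show that it must.

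It can further be said that no planned endpoint uses the code. Section 11.4 requires 24-hour reporting of all SAEs and follow-up of all AEs whatever the relationship, and single-cause attribution is a recognised convention. These points limit the consequence. They do not reconcile a section that asks for an assessment it does not define, nor remove a rule that can override its own threshold.

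**Conclusion.** The point holds in a limited form. Section 11.1.1 contradicts itself on whether procedure-relatedness is assessed and gives no definition for it. It also bars joint attribution even when an event meets the reasonable-possibility threshold for the drug. Causality data can therefore differ between sites for the same kind of event, and any mixed-cause event loses one attribution.

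The damage is confined to relatedness data and whatever reporting depends on attribution. How much reporting does so is unclear, because the sentence in section 11.1 is general. Event recording, the two AE endpoints and the endothelial cell density result do not change. The size in this study cannot be computed from the documents, and the EOP1002 figures should be cited only as an extreme case. The conclusion assumes that the CRF does not already collect the two causes separately. The change is worth making because the study is single-arm, its question is about the injections, and the cost is small.

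**What to change.** Reconcile section 11.1.1 so that one scope applies throughout.

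- Replace the closing sentence with two independent items per event: related to study drug, yes/no; related to injection procedure, yes/no. State that both may be yes.
- Reword Related and Not Related so that the reasonable-possibility test applies to each item separately. State that the injection procedure is not an alternative etiology that rules out the drug, and the reverse.
- In the data analysis plan, specify that any relatedness table shows drug, procedure, both and either. The either count is closest to the study's question.

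The cost is a wording change and one extra field on the AE page. The drug-related count may become slightly less favourable, because mixed-cause events would no longer be removable from it. No endpoint, visit or sample size changes.
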